#### 7.4 STUDY RATIONALE

Non-adherence to antipsychotic medication is a well-established risk factor for symptomatic relapse. LAI antipsychotics can improve treatment adherence, but at the time of this study there were, to our knowledge, no study on the effect of LAI antipsychotics on the policy- and cost-relevant endpoint of 30-day hospital readmission rates.

The primary hypothesis was that treatment with aripiprazole once monthly would result in lower hospitalization rates for psychiatric symptom recurrence than patients experienced prior to treatment with aripiprazole once monthly.

The secondary hypotheses were that treatment with aripiprazole once monthly would result in fewer unscheduled psychiatric emergency department (ED) visits, ED visits associated with psychiatric hospitalization, and fewer total psychiatric hospitalization days than patients experienced prior to treatment with aripiprazole once monthly. In addition, we hypothesize that clinical functioning, measured by CGI-S and CGI-I scores, and change from baseline in measures of cardiometabolic risk (CMR) such as weight, body mass index (BMI), fasting glucose, and glycosylated hemoglobin (HbA1c) would improve from baseline in patients treated with aripiprazole once monthly that were previously treated with oral antipsychotics.

The study design, following well-characterized subjects for 180 days after starting aripiprazole once monthly treatment, and retrospectively reviewing data regarding prior hospitalizations, psychiatric ED visits, and prior total psychiatric hospitalization days, will allow the proposed hypotheses to be tested.

Final; 26 Feb 2018 Page 20 of 80

ClinicalTrials.gov Identifier: NCT02717130

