# 9.1.2 Screening Period

All recruitment methods conformed to the guidelines of the IRB at the clinical site. The subjects participating in this study had to be capable of understanding the nature of the study. The ICF contained a full description of the procedures and their associated risks. Subjects were given both verbal and written descriptions of the procedures, discomforts, risks, and potential benefits by study personnel. After briefing subjects on the reasons for the research, their rights as a subject, and the risks involved, they were given the opportunity to ask questions. Subjects were asked to paraphrase the ICF. When ready, subjects were asked to give written consent to participate in the study. After the ICF was signed by both the subject and the investigator, each subject was given a copy of the signed ICF. The investigator had full responsibility for all issues pertaining to assent and informed consent. Procedures to be followed when obtaining informed consent are detailed in Section 5.1.

During the Screening Period, subjects could be treated with any oral antipsychotic medication of the clinician's choice, with the exception of clozapine. However, oral olanzapine was permitted during the Screening Period only for subjects who were eligible for Phase A.

Eligibility for the study was determined during the screening period, which could occur at any time, beginning with the first day of hospitalization. Eligibility for the study was assessed via the following:

- Confirmation of a current diagnosis of schizophrenia according to Diagnostic and Statistical Manual, Fifth Edition (DSM-5) criteria
- Review of inclusion and exclusion criteria
- Complete medical history, including demographics, complete psychiatric history including all psychiatric and non-psychiatric hospitalizations and medical interventions occurring within the 6 months prior to the date of signing the ICF:
  - O Data regarding psychiatric and non-psychiatric hospitalizations, including treatment records relevant to determination of study eligibility and identified outcome variables related to ED, outpatient and inpatient treatment episodes as described in the inclusion and exclusion criteria (Section 9.3.1 and Section 9.3.2, respectively) occurring within the 6 months prior to the date of signing the ICF were obtained by searching MO

Final; 26 Feb 2018 Page 25 of 80

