## Efficacy:

- Comparison of:
  - o 30-, 90-, and 180-day rates of unscheduled psychiatric ED visits compared with prior 30-, 90-, and 180-day unscheduled visits
  - Psychiatric ED visits plus hospitalizations compared with prior 30-, 90-, and 180-day psychiatric visits plus hospitalizations
  - Total psychiatric hospitalization days over the 30-, 90- and 180-day study period compared with the total psychiatric hospitalization days over the prior 30-, 90- and 180-day period
  - o Change from baseline in CGI-I, based on the initial CGI-S, and CGI-I scores at 30-, 90-, and 180-days
- Changes from baseline on the following indicators for CMR after receiving aripiprazole once monthly:
  - Weight and BMI
  - o Fasting glucose concentrations, HbA1c concentrations, and fasting lipids concentrations (i.e., fasting triglyceride, total cholesterol, HDL, and LDL)

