## 9.7.1.9 Efficacy Analyses

The primary objective of the study was to evaluate the effect of aripiprazole once monthly on 30-, 90-, and 180-day psychiatric re-hospitalization rates following discharge due to symptoms associated with schizophrenia, compared with retrospective 30-, 90-, and 180-day psychiatric hospitalization rates in subjects previously treated with oral antipsychotic medication.

Because all primary and secondary outcome measures described in the specific aims were continuous and a reflection of a single design configuration involving longitudinal measures, in some cases including retrospective as well as prospective time points, the basic structure of the data analytic strategies was the same for all objectives.

The primary and secondary outcomes were to be analyzed using repeated measures analysis of covariance (ANCOVA) models. For example, in the three primary outcome models, testing for a main effect of time on 30-, 90-, or 180-day pre-hospitalization (i.e., oral antipsychotic) versus 30-, 90-, or 180-day post-hospitalization (i.e., aripiprazole once monthly) rates, respectively. Covariates would have included psychiatric symptoms severity at baseline, measured by CGI-S scores.

Some secondary outcome measures such as BMI, fasting lipid parameters, and glucose that were measured at time points post-hospitalization only (i.e., at baseline, 30-, 90-, and 180-days) were to be evaluated using mixed model repeated measures analysis of variance to determine whether there are changes over time. Other covariates could include race, gender, age, family history of diabetes, and BMI.

Only one primary specific objective was defined, with three time-point comparisons (i.e., 30, 90, and 180 days) with the primary comparison being hospitalization rate for the period of 30 days pre-hospitalization (i.e., at least one, based on the index hospitalization) to 30 days post-hospitalization both because of the importance of that objective and to minimize multiple comparisons concerns. Because of the multiple comparisons issue, p-values associated with the secondary and exploratory analyses performed were to be interpreted cautiously as hypothesis-generating rather than as hypothesis-confirming.

Final; 26 Feb 2018 Page 56 of 80

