## 9.7.2 Determination of Sample Size

The primary endpoints of this study were comparisons of the rate of hospitalization for specified pre-hospitalization (i.e., pre-aripiprazole once monthly) timeframes (i.e., 30-, 90-, and 180-days) to corresponding post-hospitalization timeframes. Based on published results of other studies, it was generally reasonable to assume 30% of subjects would be hospitalized pre-medication switch and 15% would be hospitalized post-switch to aripiprazole once monthly. In this study, 100% of the pre-aripiprazole once monthly subjects would have had at least one hospitalization (i.e., index inpatient hospitalization at least). The estimated sample size of 90 completed subjects would have provided approximately 80% power (alpha = 0.05 two-sided) to detect a clinically relevant difference between pre-switch and post-switch hospitalization rates. The recent Otsuka Mirror study had 121 completers with only a 28% pre-switch hospitalization rate, compared to the present design with a 100% pre-switch hospitalization rate, with highly significant reductions in total psychiatric hospitalization rates in the Mirror study. A medium effect size = 0.5 with a sample size of N = 90 provided approximately 80% power to detect significance at the 5% level (two-tailed test).

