AIMS = abnormal involuntary movement scale, BARS = Barnes Akathisia Rating Scale, BMI = body mass index, CGI = Clinical Global Impression, ER = emergency room, HbA1c = glycosylated hemoglobin, HDL = high-density lipoprotein, LDL = low-density lipoprotein, N/A = not applicable, SARS = Simpson-Angus Rating Scale, SD = standard deviation

Note: Standard deviations not provided for Day 150 and Day 180 data due to n = 1 subject

- a: Scale = normal, not all ill (1), borderline mentally ill (2), mildly ill (3), moderately ill (4), markedly ill (5), severely ill (6), among the most extremely ill patients (7)
- b: Scale = very much improved (1), much improved (2), minimally improved (3), no change (4), minimally worse (5), much worse (6), very much worse (7)
- c Scale = none (0), minimal, maybe extreme normal (1), mild (2), moderate (3). Severe (4)
- d: Only 1 subject had ER visits (n = 3) and psychiatric hospitalizations (n = 1)

Final; 26 Feb 2018

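### The secondary composite of ED visits plus hospitalizations has no rule for an ED visit that ends in admission, and it does not match the hypothesis in Section 7.4

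*Combined protocol and SAP*

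**What the plan says.** The composite has the same wording in the Synopsis objectives, Section 8.2 and Section 9.7.1.2: "Psychiatric ED visits plus hospitalizations compared with prior 30-, 90-, and 180-day psychiatric visits plus hospitalizations". The second half drops the ED qualifier from the comparator visits. None of these places gives a unit (count, rate or share of subjects with any event), an episode definition, or a rule linking an ED visit to the admission that follows it.

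The ED endpoint listed beside it is "30-, 90-, and 180-day rates of unscheduled psychiatric ED visits compared with prior 30-, 90-, and 180-day unscheduled visits". It does not set aside visits that end in admission.

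Section 7.4 gives the secondary hypotheses as "fewer unscheduled psychiatric emergency department (ED) visits, ED visits associated with psychiatric hospitalization, and fewer total psychiatric hospitalization days". The middle item is a subset of ED visits, not a sum of ED visits and admissions.

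Three places bear on the unit:
- Section 9.7.1.9 begins its analysis rationale with "Because all primary and secondary outcome measures described in the specific aims were continuous" and applies repeated measures ANCOVA.
- Section 9.7.1.10 compares hospital stays counted per subject.
- Table 8 reports ER visits and psychiatric hospitalizations as separate totals per subject.

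On the look-back, Section 9.1.2 collects "identified outcome variables related to ED, outpatient and inpatient treatment episodes" for the six months before consent. Sections 9.7.1.9 and 9.7.2 state that the index hospitalization gives every subject at least one admission before the switch.

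**The concern.** A psychiatric relapse often generates two records, an ED visit and then an inpatient stay. If the two counts are simply added, the same relapse scores differently according to how the patient reached the ward. A change in the composite then mixes a change in the number of crises with a change in their route into care.

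The mismatch with Section 7.4 is a separate problem. An analyst could compute the sum, a de-duplicated episode count, or ED visits that led to admission, and each could be defended from some part of the document. The choice would be open after the data were seen.

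The two periods are also not alike. Every subject enters through an inpatient stay, so the pre-switch window contains that stay and possibly the ED visit that led to it. Nothing by design places a matching event after the switch.

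**Working it through.** The plan gives no rate, effect size or power for the composite, so there is no stated figure to reproduce. The check is a counting identity with illustrative inputs.

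**Notation (per subject).** e = ED visits not ending in admission; a = admissions through the ED; d = direct admissions; h = a + d; q = a/h.
- Literal sum: e + 2a + d = e + h(1 + q)
- One count per episode: e + a + d = e + h
- Section 7.4 quantity: a = qh

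**Inputs.** Section 9.7.2 says "it was generally reasonable to assume 30% of subjects would be hospitalized pre-medication switch and 15% would be hospitalized post-switch". These are shares of subjects, and the same section says that all subjects in this design have a pre-switch admission. They are used below only as illustrative admissions per subject, 0.30 before and 0.15 after. The documents give neither q nor e. I take q from 0 to 1, the same in both periods, and e = 0.30, unchanged.

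**Effect of q.** The sum's pre-post difference is 0.15 × (1 + q). The episode difference is always 0.150 and its relative reduction is 0.15/0.60 = 25.0%.

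| q | Sum, pre to post | Difference | Relative reduction, sum |
|---|---|---|---|
| 0 | 0.600 to 0.450 | 0.150 | 25.0% |
| 0.5 | 0.750 to 0.525 | 0.225 | 30.0% |
| 1 | 0.900 to 0.600 | 0.300 | 33.3% |

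At q = 1, the Section 7.4 quantity falls from 0.30 to 0.15, or 50%. The three definitions therefore give 33%, 25% and 50% on the same events.

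**Sensitivity to e, at q = 1.** With e = 0.1, the reduction is 42.9% for the sum and 37.5% per episode. With e = 0.5, it is 27.3% and 18.8%.

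**The direction can reverse.** Keep e = 0.30 and a = 0.30 fixed and let direct admissions fall from 0.30 to 0.15. The sum goes from 0.30 + 0.60 + 0.30 = 1.20 to 1.05, a fall of 12.5%. Episodes go from 0.90 to 0.75, a fall of 16.7%. Here the sum understates the relative change.

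**Index episode.** The look-back runs to consent, and screening takes place during or immediately after the hospitalization (Section 9.1), so an ED visit leading to the index admission precedes consent. The index episode adds 1 to the literal sum if the admission was direct and 2 if it came through the ED. As an example with no change at all, let non-index events be e = 0.30 and a = 0.15 in both periods, giving a sum of 0.30 + 2 × 0.15 = 0.60 each time. With the index episode in the pre count, the apparent reduction is 1 − 0.60/1.60 = 62.5% (direct) or 1 − 0.60/2.60 = 76.9% (through the ED). Taking out the admission but leaving its ED visit still gives 62.5%.

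**Table 8.** Footnote d reports one subject with three ER visits and one hospitalization. The sum is 4. Episodes are 3 if the admission followed one of those visits and 4 if it was direct. The Section 7.4 quantity is 1 or 0 respectively. The route is not reported.

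**The case against.** The strongest defence is that the plan never says linked events score twice. It leaves the unit open, and Section 7.4 could be loose wording for a linked ED-and-admission event, in which case nothing is counted twice. This stands in part: the defect is a missing rule and a mismatch between sections, and the score of 2 follows only from the literal count reading. That reading is nevertheless the one that Sections 9.7.1.9 and 9.7.1.10 and Table 8 favour.

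A second defence is that the rationale is cost and service use, for which counting ED and inpatient contacts separately is legitimate. That is fair, but the plan should then say so, and Section 7.4 should match. Admissions and unscheduled ED visits are already separate endpoints.

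Third, counting the index admission before the switch is the plan's stated design for the primary comparison. That stands, and the change proposed here is confined to this composite.

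A reader might infer four stronger claims that the documents do not support:
- That any change in admissions is counted twice, or that the composite holds the primary outcome at double weight. Direct admissions count once, and the weight reaches 2 only if every admission comes through the ED.
- That the sum overstates the treatment effect whenever admissions fall more than ED-only visits. The counterexample above shows the opposite.
- That the Table 8 subject is overcounted by a third (4 against 3). This needs an admission route that is not given, and Table 8 reports no composite.
- That every index admission came through the ED. No section says so.

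Finally, the endpoint carries no power claim, and Section 9.7.1.9 says "p-values associated with the secondary and exploratory analyses performed were to be interpreted cautiously as hypothesis-generating". This limits the consequence without supplying the rule.

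**Conclusion.** The point holds as a gap in definition and an inconsistency between sections. The composite has no rule for an ED visit that ends in admission, and no listed endpoint measures the middle hypothesis of Section 7.4. On the literal count reading, an admission weighs 1 + q, so the pre-post difference due to admissions is inflated by a factor of 1.0 to 2.0 when q is the same in both periods. The effect on the relative reduction can go either way: 33% against 25% in the illustration with all admissions through the ED, and 12.5% against 16.7% where only direct admissions fall. These percentages rest on assumed values of e, q and admissions per subject.

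The index episode is the more systematic part. It adds one or two selection-driven events to each subject's pre count, with no guaranteed counterpart after the switch. This assumes that the treatment of the index admission in Sections 9.7.1.9 and 9.7.2 carries over to the composite. No text says otherwise, and Section 9.7.1.9 applies one analytic structure to all objectives.

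The Synopsis and Section 9.7 state that no efficacy analysis was performed, so no reported result is affected.

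**What to change.** For this composite only:

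1. Define it as the number of acute psychiatric episodes per subject in each window.
2. Count an ED visit that ends in admission once, as a hospitalization, using a linkage window fixed in advance (for example same or next day; the documents give none).
3. Apply the same rule to the retrospective and prospective periods.
4. Leave the index episode, meaning the admission together with any ED visit that led to it, out of the pre count. At the least, report the composite with and without it.
5. Keep ED visits and admissions as separately reported components.
6. Align the Synopsis, Section 7.4, Section 8.2 and Section 9.7.1.2, and restore the ED qualifier in the comparator. If ED visits leading to admission are of interest in their own right, list them as an endpoint.

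The cost is revised wording plus a date-matching step on the ED and inpatient episodes that Section 9.1.2 already collects. Matching may be incomplete where events are confirmed only through caregivers, which Sections 9.1.2 and 9.5.1.3 allow. Composite counts will be smaller, and so will the apparent reduction once the index episode is removed.

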## 9.7.1.3 Exploratory Endpoints

#### Safety:

- AEs
- Clinical laboratory tests (i.e., hematology, fasting clinical chemistry, prolactin and urinalysis)
- Vital signs
- PSP
- Injection site reaction (i.e., localized pain, redness, swelling, and induration)
- C-SSRS for suicidality
- EPS assessments, including:
  - o AIMS

Final; 26 Feb 2018 Page 53 of 80

- o SAS
- o BARS

## 9.7.1.4 Definitions of Analysis Sets

Enrolled Sample: All subjects who signed an informed consent form for the study.

Phase A Safety Sample: All subjects who took at least one dose of oral aripiprazole in Phase A and had at least one post-dose safety assessment.

Phase B Safety Sample: All subjects who received at least one dose of aripiprazole once monthly in Phase B.

Phase B Efficacy Sample: The core dataset for all outcome or efficacy analyses was to be the intent-to-treat (ITT) dataset that was to consist of data from all subjects entering Phase B. However, as described in Section 9.7.4.1, in order to handle missing data and restrictions imposed by different types of analyses (e.g., change from baseline), other datasets derived from the ITT dataset could be used for the efficacy analyses.

## 9.7.1.5 Subject Disposition

The method for summarizing the number (i.e., percentage) of subjects who were screened for the study (i.e., enrolled subjects, or those who signed informed consent) and reasons for screen failure were documented in full using the dedicated Washington University REDCap file for this study, with data fields for Enrollment Tracking, Screen Visits, Screen Failures, and Subject Visit Tracking. These REDCap data fields provided a clear accounting of all subjects who entered the study, the number of subjects screened for inclusion, and a breakdown of the reasons for excluding subjects during screening. In addition, pre-enrollment general pre-screening failures were tracked.

Non-identifying or random numbers were used to identify subjects on the Screening Log and Screen Failure logs. Consented Subjects who met inclusion and exclusion criteria were entered on the Enrollment log with an assigned study number. Completion of each study visit for enrolled subjects through completion of study was documented on the Subject Visit Tracking Log. Subjects not completing the study with a description of the reason for discontinuation were documented on the Subject Visit Tracking Log.

The Excel format of these forms allowed data to be analyzed by investigators at any time during the study and to report progress to the sponsor and regulatory agencies.

## 9.7.1.6 Demographic and Other Baseline Characteristics

Baseline demographic characteristics including age, race, ethnicity, gender, weight, height and BMI were to be summarized by descriptive statistics (i.e., frequency, mean, median, standard deviation [SD], maximum, minimum, and percentage when applicable).

Baseline disease severity and psychiatric history was also summarized by descriptive statistics.

Final; 26 Feb 2018 Page 54 of 80

## 9.7.1.7 Prior and Concomitant Therapy

The Phase B Efficacy set was used.

## 9.7.1.8 Safety Analyses

All safety analyses were to be performed on the Safety Analysis Sets. Safety data were summarized on an "as treated" basis using descriptive statistics (e.g., n, mean, standard deviation, median, minimum, maximum for continuous variables; and n [%] for categorical variables). Safety variables included TEAEs, clinical laboratory parameters, vital signs, and 12-lead ECG results. Study Day 1 for all safety analyses was defined as the date of the first dose of study drug.

In general, baseline measurements of safety variables were defined as the last measurements prior to the first dosing of study drug for each phase of the study. Safety analyses were conducted based on the safety populations (Section 9.7.1.4).

#### 9.7.1.8.1 Adverse Events

The AE verbatim descriptions (i.e., investigator terms from the CRF) were to be recorded and entered into the database.

A TEAE was defined as an AE that emerged during treatment, having been absent at pretreatment (i.e., baseline) or

- Reemerged during treatment, having been present at pretreatment (i.e., baseline) but stopped before treatment
- Worsened in severity during treatment relative to the pretreatment state, when the AE was continuous.

Only those AEs that were treatment emergent were to be included in summary tables. All AEs, treatment emergent or otherwise, were presented in subject data listings.

Treatment-emergent AEs were summarized. The incidence of TEAEs was reported as the number (i.e., percentage) of subjects with TEAEs by system organ class and preferred term (PT). A subject was counted only once within a system organ class and PT, even if the subject experienced more than one TEAE within a specific system organ class and PT. The number (i.e., percentage) of subjects with TEAEs was also summarized by maximum severity (i.e., mild, moderate, or severe).

The number (i.e., percentage) of subjects with TEAEs were also summarized by relationship to study drug (i.e., possibly related, probably related, and not related).

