#### **Assessing Severity of Adverse Events**

AEs were graded on a 3-point scale (i.e., mild, moderate, and severe) and reported in the detail indicated on the CRF. The definitions were as follows:

Mild: Discomfort noticed, but no disruption of normal daily activity

Final; 26 Feb 2018 Page 41 of 80

Moderate: Discomfort sufficient to reduce or affect normal daily activity

Severe: Incapacitating, with inability to work or to perform normal daily activity

The criteria for assessing severity are different than those used for seriousness (see Serious Adverse Events and Other Events of Interest [Section 9.5.1.6] for the definition of an SAE).

The causal relationship of the study drug to an AE was assessed as related or unrelated, as follows:

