#### Related:

Definite: There was a reasonable causal relationship between the study drug and the AE,

when the event responded to withdrawal of the study drug (i.e., dechallenge),

and recurred with rechallenge by administration of the study drug.

Probable: There was a reasonable causal relationship between the study drug and the AE.

The event responded to dechallenge. Rechallenge was not required.

Possible: There was a reasonable causal relationship between the study drug and the AE.

Dechallenge was lacking or unclear.

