#### Unrelated:

Not Likely: There was a temporal relationship to study drug administration, but there

was not a reasonable causal relationship between the study drug and the

event.

Not Related: There was not a temporal or causal relationship to the study drug

administration.

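### The planned summary of treatment-emergent adverse events by relationship has no row for events graded Definite, the strongest related grade collected

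*Combined protocol and SAP*

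**What the plan says.** **Collection.** Section 9.5.1.5, at the end of the text on assessing severity, sets two groups: "The causal relationship of the study drug to an AE was assessed as related or unrelated, as follows". Three grades then stand under Related:

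- "Definite: There was a reasonable causal relationship between the study drug and the AE", with the further conditions that the event resolved on withdrawal and came back on rechallenge.
- "Probable: There was a reasonable causal relationship between the study drug and the AE", with response to withdrawal but no rechallenge needed.
- "Possible: There was a reasonable causal relationship between the study drug and the AE", with withdrawal information absent or unclear.

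Two grades stand under Unrelated:

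- "Not Likely: There was a temporal relationship to study drug administration", but without a reasonable causal link.
- "Not Related: There was not a temporal or causal relationship to the study drug".

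**Analysis.** Section 9.7.1.8.1 plans three TEAE summaries, each as a number and percentage of subjects: by system organ class and preferred term, by maximum severity, and by relationship. For the last, the categories are "possibly related, probably related, and not related", introduced by *i.e.* The same section sends all AEs to the subject data listings.

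**The concern.** The analysis rule does not fit the data it is meant to summarise. The grade with no row is the one that needs the most evidence of causation: improvement off drug and recurrence on re-exposure. A programmer working from section 9.7.1.8.1 would either leave Definite events out of the relationship table or choose a row for them without a documented rule.

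The study is single-arm and unblinded (sections 9.4.3 and 9.4.4). With no control group to compare against, the investigator's causality grade carries more of the weight when the safety data are read, so the table that displays it should cover every grade.

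**Working it through.** No sample size, power or error rate is involved, and there is no planned figure to reproduce. The check matches each grade collected in section 9.5.1.5 to a category in section 9.7.1.8.1.

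| Grade collected | Group | Row, labels taken literally | Row, if the third label means the whole Unrelated group |
|---|---|---|---|
| Definite | Related | none | none |
| Probable | Related | probably related | probably related |
| Possible | Related | possibly related | possibly related |
| Not Likely | Unrelated | none | not related |
| Not Related | Unrelated | not related | not related |

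1. Literal reading: 5 grades collected, 3 matched, 5 − 3 = 2 without a row (Definite and Not Likely).
2. Generous reading: 5 grades collected, 4 matched, 5 − 4 = 1 without a row (Definite).
3. Definite has no row on either reading, so that gap does not depend on how the third label is understood.

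**Is the list meant to be complete?** It is introduced by *i.e.* In the same section, the severity summary uses the same form for mild, moderate and severe, and that list reproduces all three severity grades defined in section 9.5.1.5. Section 9.7.1.8 uses *e.g.* where it gives sample descriptive statistics. The natural reading is that the relationship list was also meant to be complete.

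**Who would be affected?** The summary counts subjects.

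- A subject whose only TEAEs are Definite would be absent from the table.
- A subject with a Definite TEAE and another TEAE in a listed grade would appear, but only under the weaker grade.

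**Where do the events remain?** The system organ class and preferred term summary and the maximum-severity summary do not depend on causality, so a Definite TEAE counts in both. It also appears in the listings.

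**The case against.** The other side has a good case on scope and consequence.

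- **Two of five grades dropped.** A reader might infer this from the literal count. The text does not establish it. Section 9.5.1.5 puts Not Likely and Not Related together under Unrelated, so the third category can fairly be read as that whole group. Not Related is also a grade in its own right and no collapsing rule is given, so Not Likely is ambiguous rather than dropped.
- **Definite events lost from safety reporting.** A reader might infer this too. It is not so: they stay in the other two TEAE summaries and the listings.
- **Rows that fail to add up to all TEAEs.** This does not follow, because the table counts subjects rather than events. The severity summary takes each subject's maximum, but the relationship summary has no equivalent rule. A subject could fall in several rows, and the counts need not add to a fixed total even with five rows.
- **Drug-related harm understated.** Section 9.7.1.8.1 plans no pooled related total. If one were made, the grouping in section 9.5.1.5 would place Definite within it. An undercount would arise only if someone built the total by adding the possible and probable rows.
- **Small yield.** Definite requires recurrence on rechallenge. No rechallenge procedure is planned, and section 9.3.3.3 withdraws subjects whose AE is judged to warrant it. Recurrence after repeated dosing remains possible, so the grade cannot be assumed empty.
- **Nothing turned on it.** Safety endpoints are exploratory and descriptive, 9 subjects were recruited, and the Synopsis states that safety was not analysed.

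These points limit the finding to one grade in one table and make it minor. They do not supply a row for Definite.

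**Conclusion.** The point holds for Definite: the planned relationship summary omits a grade that the plan itself defines and collects, and no section available for review maps it elsewhere. Severity is minor. One descriptive table is affected, the same events are visible in other planned outputs, and no analysis or decision in this terminated study is shown to depend on it.

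Two limits apply. The number of Definite TEAEs is not in the documents. The report's adverse event table (Table 6 in the list of in-text tables) is not in the text available for review, so how relationship was actually displayed cannot be checked.

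The conclusion assumes that the case report form recorded the five grades as section 9.5.1.5 defines them. If it recorded only related or unrelated, the three-category list would still not fit, because possible and probable could not be told apart.

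**What to change.** In section 9.7.1.8.1, replace the three-category list with a rule to this effect: TEAEs are summarised as related (definite, probable, possible) or unrelated (not likely, not related), and each subject is counted once, at the strongest relationship among that subject's TEAEs.

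This settles Definite, removes the ambiguity over Not Likely, and gives the relationship summary the same one-count-per-subject logic that the severity summary already has. Showing the five grades as sub-rows is optional.

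The cost is one sentence. It uses the plan's own grouping and needs no new data. Counting at the strongest relationship means that a subject's weaker-graded events do not show separately in this table, but they remain in the listings. Because the study has ended, the change matters for any later tabulation of these data and for any plan that reuses this text.
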